# 5. Handling of Missed Assessments/Visits/Doses

Relevant study data elements impacted by a pandemic or other emergency situations should be documented (eg, "COVID-19-related" or in accordance with Sponsor recommendations) in CRFs and/or other study systems, as directed by Sponsor guidance; these may include missed/delayed/modified study visits/assessments/dosing, and instances where temporary measures such as those above are implemented.

# 6. Management of Participants Infected With SARS-CoV-2

If a participant develops SARS-CoV-2 infection or related disease, the investigator should contact the Sponsor to discuss plans for study intervention and follow-up. An interruption of study treatment should be considered by the investigator, depending on symptoms and concomitant medication used for the treatment of COVID-19. Treatment must be interrupted if prohibited medication is used. Standard adverse event and serious adverse event reporting requirements apply.

When a participant for whom study treatment has been interrupted recovers from suspected or confirmed SARS-CoV-2 infection or related disease and all toxicities improve to Grade  $\leq 1$ , the investigator should discuss with the Sponsor about resuming study treatment.

Consenting and re-consenting of participants will be performed as applicable for the measures taken (including remote consenting by phone or video consultation) and according to local guidance for informed consent applicable during the COVID-19 pandemic.

# 7. Statistical Considerations

Statistical analysis will be done by the Sponsor or under the authority of the Sponsor. A general description of the statistical methods to be used to analyze the efficacy and safety data is detailed in the protocol.

The Sponsor will evaluate the totality of impact of the restrictions and limitations arising from a pandemic on collection of key study data and additional data analyses will be outlined in the Statistical Analysis Plan(s).

In line with the protocol Section 8.9.2. the sample size may be further revised to compensate for major protocol deviations during a pandemic which could potentially impact the primary endpoint. The new sample size will also account for any future dropouts.

Note: In case of emergency situations where the recommendations specified in this protocol are insufficient, the investigator or site-staff are instructed to follow local guidelines and recommendations, or contact the Sponsor for guidance.

7. F	REFERENCES	47

VERSION HISTORY

Table 1 – SAP Version History Summary

SAP Version	Approval Date	Change	Rationale
1.0	21 Jul 2023	Not Applicable	Initial release

1. INTRODUCTION

This statistical analysis plan (SAP) contains the definitions of analysis sets, key derived variables, and statistical methods to evaluate the safety and efficacy of guselkumab in adult participants with moderate to severe plaque psoriasis Protocol CNTO1959PSO4015. Analysis results titles, mockups, and programming instructions for all statistical outputs (tables, figures, and listings) will be provided in a separate document entitled Data Presentation Specifications (DPS).

This current SAP covers the analyses to be performed following the Sponsor decision to prematurely terminate the study on 31 MAY 2023 due to slow enrollment.

1.1. Objectives and Endpoints

Objectives	Endpoints	
Primary		
To evaluate the effect of guselkumab on Coronary flow reserve (CFR) measured by transthoracic doppler-echocardiography, in participants with moderate-to-severe psoriasis and intermediate cardiovascular risk*	Change from baseline [†] in Coronary Flow Reverse (CFR) at Week 32	
Secondary		
To evaluate the short-term effect of guselkumab on CFR measured by transthoracic doppler echocardiography, in participants with moderate-to-severe psoriasis and intermediate cardiovascular risk.	Change from baseline in CFR at Week 16.	
To evaluate the effect of guselkumab on Global Longitudinal Strain (GLS) as a surrogate marker of left ventricular function in participants with moderate-to-severe psoriasis and intermediate cardiovascular risk.	 Change from baseline in GLS at Week 32. Change from baseline in GLS at Week 16. 	
To evaluate the effect of guselkumab on carotid femoral pulse wave velocity (cfPWV) as a surrogate marker of arterial stiffness in participants with To evaluate the effect of guselkumab on CFR among participants in the different CFR categories.	 Change from baseline in carotid-femoral pulse wave velocity (cfPWV) at Week 32. Change from baseline in cfPWV at Week 16. Change from baseline in CFR at Week 16 and Week 32 among participants with CFR in the ranges of 2 to 2.74, and 2.75 to 3.5 at baseline. 	

To evaluate the effect of guselkumab on surrogate CV risk markers among nicotine users and non-users in the participant population

- Change from baseline in CFR at Week 16 and Week 32 among nicotine users and non-users.
- Change from baseline in GLS at Week 16 and Week 32 among nicotine users and nonusers.
- Change from baseline in cfPWV at Week 16 and Week 32 in nicotine users and nonusers.

The G-CARE study will also investigate the following exploratory objectives:

- To evaluate the correlation between skin improvement and cardiovascular risk surrogate markers in participants with moderate-to-severe psoriasis and intermediate cardiovascular risk.
- To evaluate the effect of guselkumab on disease-related quality-of-life in participants with moderate-to-severe psoriasis and intermediate cardiovascular risk.
- To evaluate the effect of guselkumab on quality of sleep, alcohol intake patterns and depression and anxiety in participants with moderate-to-severe psoriasis and intermediate cardiovascular risk.
- To evaluate the effect of guselkumab on biomarkers in participants with moderate-to-severe psoriasis and intermediate cardiovascular risk.

1.2. Study Design

This is an interventional, single-arm, open-label, oligocentric study to evaluate the effect of guselkumab on cardiovascular risk surrogate markers in adult men and women diagnosed with moderate-to-severe plaque psoriasis (with or without psoriatic arthritis [PsA]) for at least 6 months prior to study entry. Participants will be assessed for eligibility at 2 screening visits; at Screening Visit S1, dermatology, medical history, and laboratory parameters will be assessed. Participants fulfilling eligibility criteria at Screening Visit S1 will be referred to the cardiology department and will undergo cardiologic assessments (cfPWV, GLS and CFR [via transthoracic doppler echocardiography]) at Screening Visit S2, and again at Week 0. Only participants with CFR \geq 2 and \leq 3.5 at both these time-points will be enrolled in the study. The CFR measurement at Week 0 will be considered as the baseline value.

An overview of the intervention study is presented in Figure 1 below:

^{*} Intermediate cardiovascular risk defined by CFR \geq 2 and \leq 3.5 at Screening Visit S2. † cfPWV, GLS and CFR measurements at Week 0 will be considered as the baseline value. CFR must not be \leq 2 or \geq 3.5 at both Screening Visit S2 and Week 0.

Open-label Treatment Phase END OF STUDY 20 16 28 32 40 S1 Derm **S2** Cardio PE Treatment Cohort: Nicotine Users (n=20) Nicotine Non-users (n=30) = Cardiology Assessments (cfPWV, GLS and CFR) = Biomarker Assessments Visit Window between Screening Visit 1 and Screening Visit 2 = maximum of 2 weeks $Visit\ Window\ between\ Screening\ Visit\ 2\ and\ Week\ 0=minimum\ of\ 2\ weeks\ and\ maximum\ of\ 4\ weeks\ CFR,\ GLS\ and\ cfPWV\ measurements\ at\ Week\ 0\ will\ be\ considered\ as\ the\ baseline\ measurements\ at\ Week\ 0\ will\ be\ considered\ as\ the\ baseline\ measurements\ at\ Week\ 0\ will\ be\ considered\ as\ the\ baseline\ measurements\ at\ Week\ 0\ will\ be\ considered\ as\ the\ baseline\ measurements\ at\ Week\ 0\ will\ be\ considered\ as\ the\ baseline\ measurements\ at\ Week\ 0\ will\ be\ considered\ as\ the\ baseline\ measurements\ at\ Week\ 0\ will\ be\ considered\ as\ the\ baseline\ measurements\ at\ Week\ 0\ will\ be\ considered\ as\ the\ baseline\ measurements\ at\ week\ 0\ will\ be\ considered\ at\ the\ baseline\ measurements\ at\ week\ 0\ will\ be\ considered\ at\ the\ baseline\ th$ cfPWV = carotid-femoral pulse wave velocity: CFR = coronary flow reserve; GLS = global longitudinal strain; PE = Primary Endpoint; S1 = Screening Visit 1 (Dermatology Assessments); S2 = Screening Visit 2 (Cardiology Assessments); SE = Secondary Endpoint

Figure 1: Schematic Overview of Study Design

The study is prematurely discontinued on 31st of May 2023,

- All data collected will be analyzed and therefore, all data will need to go through data cleaning process.
- Before the 31st of May 2023, per protocol visits can be scheduled, this allows sites to decide for continued patient treatment, either on commercial guselkumab or any other treatment
- o After the 31st of May 2023 only the Final Efficacy visits, and Final Safety visits are to be scheduled.
- There are instances where the sponsor recommends not to do the per-protocol visits prior to 31st of May in case this results in too much patient burden in terms of assessments e.g., 2 cardiovascular assessments in a short timeframe.

2. STATISTICAL HYPOTHESES

The primary hypothesis of this study is that guselkumab (administered as 100 mg at Weeks 0, 4, 12, 20 and 28) is effective in reducing surrogate markers of cardiovascular risk as assessed by the change from baseline of CFR measurement at Week 32 (i.e., change from baseline of CFR measurement at Week 32 is positive).

3. SAMPLE SIZE DETERMINATION

The initial sample size calculation was based on the assumption that participants will show an average increase of 20% in CFR at Week 32. To detect a CFR, mean change of 0.3 from baseline with 80% power, and assuming a standard deviation of 0.8 and a 5% dropout rate, 50 participants are expected to be enrolled in the study. Sample size may be increased if the dropout rate is higher than expected, in accordance with the sample size assumptions stated above.

After the decision to prematurely terminate the study, this sample size calculation was no longer relevant.

4. POPULATIONS (ANALYSIS SETS) FOR ANALYSIS

Analysis Set	Description
Screened	All participants who signed the informed
	consent form (ICF).
Full Analysis Set (FAS)	The FAS includes all participants who
	received at least 1 dose of guselkumab.
Safety Analysis Set	The safety analysis set includes all
	participants who received at least 1 dose of
	adenosine and guselkumab.

5. STATISTICAL ANALYSES

5.1. General Considerations

Descriptive statistics (eg, mean, median, standard deviation (SD), minimum, and maximum) will be used to summarize continuous variables. Counts and percentages will be used to summarize categorical variables. Graphic data displays may also be used to summarize the data. In addition, graphical data displays (eg, line plots) and participant listings may also be used to summarize the data.

The summarized data will be presented by Nicotine-user, non-Nicotine user and total group.

Baseline Value: For all endpoints the last non-missing measurement prior to or on the day of the first administration of the study treatment (guselkumab) will be the Baseline value in the study (i.e., at 'Week 0, Baseline' analysis visit, following assignment of the actual visits using visit windows, as indicated in Table 2).

Level of Significance: In general, all tests will be performed at a 2-sided significance level of 0.05, unless otherwise specified. All interval estimations will be reported using 2-sided 95%CI. Nominal p-values will be presented.

Change from Baseline:

For the continuous variables pertaining to the cardiology outcomes, skin related outcomes, or paper PRO outcomes the determination of change from baseline will be determined only when both, baseline and the measurement for the particular visit is available.

Change from Baseline at visit x = Measurement from the visit x - Baseline value of the parmeter

The number of patients with missing change from baseline values will be also presented in the statistical outputs.

For continuous or ordinal efficacy endpoints, a Mixed-effect Model for Repeated Measures (MMRM) will be used. Covariates such as Nicotine use, body mass index (BMI), presence, or absence of PsA, age, gender, and visit will be incorporated into these models.

For binary efficacy endpoints, 95% confidence interval [CI] for binomial proportions will be provided using exact methods, such as Clopper-Pearson or Chan-Zhang.

5.1.1. Visit Windows

Baseline will be defined as the last non-missing measurement prior to or on the day of the first dose of study treatment (guselkumab).

Study day will be calculated as follows:

- Days prior to first dose: Study Day = date treatment first dose date.
- Days on or after first dose: Study Day = date treatment first dose date + 1.

First dose refers to guselkumab.

As participants do not always adhere to the protocol visit schedule, the following rules are applied to assign actual visits to analysis visits. Listed below are the visit windows and the target days for each visit. The reference day is Study Day 1. If a participant has 2 or more actual visits in 1 visit window, the visit closest to the target day will be used as the protocol visit for that visit window. The other additional visit(s) will not be used in the summaries or analyses but they can be used for determination of clinically important endpoints. If 2 actual visits are equidistant from the target day within a visit window, the later visit is used.

The Time Interval (label on output), Time Interval (Day) and the Target Time Point (Day) are indicated in Table 2. If an assessment is not scheduled for every visit, windows will be combined so that the interval between targeted study days is split evenly and consistently between visits.

Table 2: Visit Windows

Scheduled Visit	Time Interval (label on	Planned	Target Time Point	Time Interval	Target Time
Number	output)	Time Point	(Interval for tests)	(Day) *	Point (Day) *
			-42 – -28		
			(Only for		
			pregnancy test)	-42 – -28	-
			-42 – -14		
			(Only for clinical		
			laboratory tests and		
			vital signs [blood		
			pressure,	-42 – -14 (Prior to	
			pulse/heart rate and	Screening	
			temperature])	Visit S2)	-
			- 56 – - 1		
		Screening	(Only for		
		Visit S1	QuantiFERON-TB		
		(Dermatology)	Gold test)		
		(Maximum of	(Within 2 months		
		2 weeks prior	before		
	Screening	to Screening	Week 0)	- 56 – - 1	-
S1	Visit S1	Visit S2)	-841	-841	-

CONFIDENTIAL – FOIA Exemptions Apply in U.S.

	Time				
Scheduled	Interval				
Visit	(label on	Planned	Target Time Point	Time Interval	Target Time
Number	output)	Time Point	(Interval for tests)	(Day) *	Point (Day) *
			(Only for Chest		
			radiograph)		
			(Within 3 months		
			before		
			Week 0)		
			-42 – -14	-4214	-
		Screening			
		Visit S2	07 14		
		(Cardiology)	-27 – -14		
		(Minimum of 2 weeks and	(Only for		
		maximum of 4	pregnancy test, urine nicotine test,		
	Caranina				
S2	Screening Visit S2	weeks prior to Week 0)	cfPWV, GLS and CFR)	-27 – -14	
32	v 1511 52	vv cck U)	CI'N)	≤ 1 (Pre-dose based	_
				on the time of the	
				assessment if	
				applicable) ^a	1
				-13 – 1 (Pre-dose	1
				based on the time	
				of the assessment if	
				applicable) ^a	
		Treatment			
	Week 0,	Phase:		(For cfPWV, GLS	
1	Baseline	Week 0	1 (Pre-dose)	and CFR)	1
		Treatment		2 – 57 (Pre-dose	
		Phase:		based on the time	
		Week 4 (±7		of the assessment if	
2	Week 4	days)	22 – 36 (Pre-dose)	applicable)	29
		Treatment		58– 99 (Pre-dose	
		Phase:		based on the time	
		Week 12 (±7		of the assessment if	
3	Week 12	days)	78 – 92 (Pre-dose)	applicable)	85
			106 – 120 (Pre-	400 :	4.5-
		Treatment	dose)	100 – 125	113
		Phase:	106 – 127 (Pre-		
		Week 16	dose)		
4	W. 1 16	(-7 to +7 or	(O.1. C. CED)	100 100	112
4	Week 16	+14 days) b	(Only for CFR)	100 – 129	113
				126 – 169 (Pre-	
				dose based on the time of the	
				assessment if	
		Treatment			141
		Phase:		applicable) 130 – 169 (Pre-	141
		Week 20 (±7	134 – 148 (Pre-	dose based on the	
5	Week 20	`	dose)	time of the	141
 	week 20	days)	uose)	time of the	141

Scheduled Visit	Time Interval (label on	Planned	Target Time Point	Time Interval	Target Time
Number	output)	Time Point	(Interval for tests)	(Day) *	Point (Day) *
				assessment if	
				applicable)	
				(O. 1. C. CED.)	
				(Only for CFR)	
				170 – 210 (Pre-	
		Treatment		dose based on the	
		Phase:		time of the	
_		Week 28 (±7	190 – 204 (Pre-	assessment if	4.0=
6	Week 28	days)	dose)	applicable)	197
		Final Efficacy	218 – 232	211 - 252 °	225
	Final	Visit:			
	Efficacy	Week 32	218 - 239		
	Visit	(-7 to +7 or			
7	(Week 32)	+14 days) b	(Only for CFR)	211 - 256 °	225
		Final Safety			
		Visit:			
		12 Weeks (±7			
		days) after the		253 - 287 d e	
		last dose of		or	
		guselkumab	77 – 91 **	77 – 91 ** (after the	
	Final	within the	(after the last dose	last dose of	
	Safety	treatment	of guselkumab	guselkumab within	281
	Visit	phase	within the	the treatment	or
8	(Week 40)		treatment phase)	phase) ^e	85 **

^{*}Relative to the day of first administration of the study treatment (guselkumab).

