At these visits, participants will undergo PASI, BSA and IGA assessments as assessed by the dermatology investigator. Safety assessments including urine pregnancy test (where applicable) will be performed per the Schedule of Activities, and adverse events and concomitant therapy will be recorded. Guselkumab will be administered only after completion of all the assessments for that time-point.

#### Study Visits Weeks 16 and 32

At Week 16 and 32, the participant will complete the PRO questionnaires (DLQI first, followed by other PROs) prior to other assessments and procedures. The dermatological investigator will review the safety assessments and concomitant medication, and enquire about nicotine use in the 12 hours prior to the visit. The physical examination will include vital signs and PASI, BSA, and IGA assessments performed by the dermatology investigator. Serum, plasma, and urine samples will be drawn. After a urine nicotine test to determine nicotine use, and a negative urine pregnancy test (if applicable), the participant will proceed to the cardiology department, where the cfPWV, GLS, CFR and other assessments will be performed in arbitrary sequence by the cardiology investigator. Participants who have been fasting for the lipid and metabolic panel are permitted to have a non-caffeinated drink prior to the cardiology assessments.

If CFR measurement is unsuccessful at any time-point during the study, eg, if the acoustic window of the coronary artery cannot be properly found, 2 attempts to measure the CFR can be made on different days. At Weeks 16 and 32, the visit window can be extended by 7 additional days (CFR visit window -7/+14 days). If all 3 attempts to obtain CFR at Week 16 are unsuccessful, the participant may still proceed the study with all the scheduled procedures. Actual dates of assessments will be recorded in the source documentation and CRF.

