## 8.1. Efficacy Assessments

Every effort should be made to ensure that the cardiology physician or designee who performed the cardiology efficacy assessments (cfPWV, GLS and CFR) for a participant at Week 0 should also perform the evaluations for the participant at Week 16 and Week 32. Every effort must be made to perform the assessments at the same lab, on the same machine, using the same software for all the visits. Assessments should be processed per the guidelines from the core lab. All CFR and GLS assessments must be recorded. The results from GLS and CFR assessments will be securely transmitted to the cardiology core lab for blinded independent review of endpoints, per guidelines laid down in the process document of the core lab. To determine eligibility, the CFR results obtained at the study site will be used. The use of contrast media for assessments is not permitted. Sites staff will be trained by the Sponsor or designee to perform the CV assessments to ensure standardization of the procedures.

The following assessments will be carried out as detailed in the Schedule of Activities. The efficacy assessments will be performed locally at the sites.

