5.2. Participant Dispositions

Screened participants and reason for screen failures will be summarized overall.

The number of participants in the following disposition categories will be summarized throughout the study by Nicotine-user, non-Nicotine user groups and overall:

• Participants enrolled (e.g., Participants who fulfilled eligibility criteria at Screening Visit S1 and with CFR ≥2 and ≤3.5 both at Screening Visit S2, and at Week 0.).

^{**} Relative to the day of last administration of the study treatment (guselkumab) within the treatment phase.

^a Baseline

^b If CFR measurement is unsuccessful, 2 attempts to measure a CFR can be made on different days. In such cases, at Weeks 16 and 32 the visit window for the CFR parameter can be extended by 7 additional days (CFR visit window = -7 / +14 days).

^c For participants, who do have a Week 28 assessment, 4 weeks after the last dose of the guselkumab within the treatment phase. For participants who permanently discontinue guselkumab before Week 28, the date of discontinuation. Following the premature termination of the study 4 to 8 weeks after the last dose of guselkumab within the treatment phase.

^d Only for participants, who do have a Week 28 assessment.

^e For participants who receive guselkumab after the treatment phase, the date of the first dose of guselkumab outside of the treatment phase.

- Participants who received study intervention (guselkumab).
- Participants who completed the study.
- Participants who discontinued study intervention (guselkumab).
 - o Reasons for discontinuation of study intervention (guselkumab).
- Participants who terminated study prematurely along with primary reasons.

Listings of participants will be provided for the following categories:

- Participants who discontinued study intervention (guselkumab).
- Participants who terminated study prematurely
- Participants who were enrolled yet did not receive study intervention (guselkumab).

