5.4.1.1.2. Carotid-femoral Pulse Wave Velocity (cf-PWV)

The measurement of cfPWV is accepted as the most simple, non-invasive, robust, and reproducible method to determine arterial stiffness.28 Carotid-femoral (cf) PWV is a direct measurement, and it corresponds to the widely accepted propagative model of the arterial system. Measured along the aortic and aorto-iliac pathway, it is the most clinically relevant since the aorta and its first branches are what the left ventricle 'sees' and are thus responsible for most of the pathophysiological effects of arterial stiffness. cfPWV is usually measured using the foot-to-foot velocity method from various waveforms. These are obtained transcutaneously at the right common carotid artery and the right femoral artery (ie, 'carotid-femoral' PWV), and the time delay (\Delta to transit time) measured between the feet of the 2 waveforms. A variety of different waveforms can be used including pressure, distension, and Doppler. The distance (D) covered by the waves is usually assimilated to the surface distance between the 2 recording sites. cfPWV is calculated as cfPWV=D (meters)/\Delta t (seconds). Average of triplicate cfPWV measurements will be derived and used for the analysis at each of the treatment time point.

Data Handling Rules for Efficacy Analyses

The secondary efficacy analyses (eg, over time summaries), after the treatment failures are applied, no imputation will be performed for missing data (eg, lost to follow-up, missed study visit) and the values will remain as missing and as observed data will be used for the analysis.

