6.2. Appendix 2 Changes to Protocol-Planned Analyses

The Safety Analysis Set is different in the Protocol.

Safety analysis set defined in the protocol as "All enrolled participants who receive at least 1 dose of guselkumab." Whereas in SAP we have modified the definition as "The safety analysis set includes all participants who received at least 1 dose of adenosine and guselkumab".

The Safety Analysis Set will likely contain more participants than the FAS. It would not be appropriate to define the safety analysis set as participants receiving at least one dose of guselkumab. It is necessary to also capture possible safety related information starting with the first assessment of the Coronary Flow Reserve at visit S2, because it involves use of intravenous Adenosine.

All enrolled participants who receive at least 1 dose of guselkumab, while it is "The full analysis set (FAS) includes all participants who received at least 1 dose of guselkumab." in the current SAP.

In Protocol the primary and secondary efficacy endpoints are performed at Week 32 for CFR, GLS and cfPWV, while in SAP it is appropriately defined to be completed at Final Efficacy Visit (Week 32) as per Table 2. The primary and secondary efficacy endpoints will be analyzed at Final Efficacy Visit (Week 32) with the definition applied as per Table 2 for the last dose after premature termination of the study.

In the protocol The Final Efficacy Visit (Week 32) should occur 4 weeks after the last dose of the guselkumab within the study. Whereas in SAP, following the premature termination of the study 4 to 8 weeks after the last dose of guselkumab within the treatment phase will be used.

In the protocol for participants who prematurely discontinues guselkumab before Week 28, the Final Efficacy Visit (Week 32) should take place at the time of discontinuation, or as soon as possible, and all assessments scheduled for the Final Efficacy Visit (Week 32) should be performed, whereas in the SAP for participants who permanently discontinue guselkumab before Week 28, the date of discontinuation will be used.

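### SAP Table 2 gives CFR a Week 20 window that the SAP's own combining rule excludes, and states no precedence between the day windows and the last-dose definition of Week 32

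*SAP*

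**What the plan says.** **When cardiology is measured.** Protocol Section 8.1 asks that the person who did the Week 0 cardiology assessments "should also perform the evaluations for the participant at Week 16 and Week 32". For Weeks 4, 12, 20 and 28, protocol Section 8 lists skin assessments as the efficacy content: "At these visits, participants will undergo PASI, BSA and IGA assessments as assessed by the dermatology investigator". The Schedule of Activities agrees: cfPWV, GLS and CFR appear only at S2 and Weeks 0, 16 and 32.

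**How readings get an analysis visit.** SAP Section 5.1.1 assigns actual visits by study day using Table 2. If two visits share a window, the one closer to target is used and the other is left out of the analyses. For assessments not done at every visit, "windows will be combined so that the interval between targeted study days is split evenly and consistently between visits".

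**What Table 2 contains.** CFR has its own rows at Week 16 (Days 100 to 129), Week 20 (Days 130 to 169) and Week 32 (Days 211 to 256). GLS and cfPWV have no post-baseline rows of their own. The general rows are Week 16 (Days 100 to 125), Week 20 (126 to 169), Week 28 (170 to 210) and Week 32 (211 to 252). The S2 row for cardiology runs from Day -27 to Day -14.

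**The second definition of Week 32.** Footnote c, attached to both Week 32 rows, defines the visit by events as well: "For participants who permanently discontinue guselkumab before Week 28, the date of discontinuation", and "Following the premature termination of the study 4 to 8 weeks after the last dose of guselkumab within the treatment phase". SAP Appendix 2 adds: "The primary and secondary efficacy endpoints will be analyzed at Final Efficacy Visit (Week 32) with the definition applied as per Table 2".

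**Missing values.** SAP Section 5.4.1.1.2 says that "no imputation will be performed for missing data"; Section 5.3.1.1 says the same.

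**The concern.** The combining rule and the table cannot both be followed for CFR. The Week 20 row is not a general row that the rule could override. It is marked as applying to CFR alone, yet it assigns the primary measure to a visit where it is neither scheduled nor an endpoint. A reading labelled Week 20 is then either left out of the model or becomes a visit level that the SAP does not describe.

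The second problem concerns the data this SAP was written for. After 31 May 2023 only Final Efficacy and Final Safety visits were to be scheduled (SAP Section 1.2). A final visit timed from the last dose can fall on a study day that Table 2 gives to Week 16, 20 or 28, while footnote c calls the same visit Week 32. Visit is a term in the MMRM and values are analysed as observed. The programmer's choice therefore decides which readings enter the primary Week 32 estimate, in a study that Appendix 2 describes as having few participants.

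The third problem is small: a permitted S2 reading can miss its window and so drop out of the S2-versus-Week 0 comparison planned in SAP Section 5.7.7.

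**Working it through.** **Inputs.** Target days from Table 2: Week 0 = 1, Week 4 = 29, Week 12 = 85, Week 16 = 113, Week 20 = 141, Week 28 = 197, Week 32 = 225, Week 40 = 281. The cut between neighbouring visits is (target a + target b)/2.

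**1. Can Table 2's cuts be reproduced from all visits?**

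| Between | Midpoint | Last day of earlier window in Table 2 |
|---|---|---|
| Weeks 4 and 12 | (29+85)/2 = 57 | 57 |
| Weeks 12 and 16 | (85+113)/2 = 99 | 99 |
| Weeks 16 and 20 | (113+141)/2 = 127 | 125 general, 129 CFR |
| Weeks 20 and 28 | (141+197)/2 = 169 | 169 |
| Weeks 28 and 32 | (197+225)/2 = 211 | 210 |
| Weeks 32 and 40 | (225+281)/2 = 253 | 252 general, 256 CFR |

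Most cuts follow the full visit schedule, with a one-day tie convention at 210 and 252. The general Week 16 end is two days below the midpoint and the CFR end two days above it.

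**2. The combining rule for cardiology.** With targets 1, 113 and 225 the cuts are (1+113)/2 = 57 and (113+225)/2 = 169. Week 16 is then Days 58 to 169 and Week 32 starts at Day 170. Against that:
- The CFR Week 20 row takes Days 130 to 169 out of Week 16: 169 - 130 + 1 = 40 days.
- If the general rows also apply, Week 12 takes Days 58 to 99 (42 days) from Week 16, and Week 28 takes Days 170 to 210 (41 days) from Week 32.

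**3. Does this touch readings taken within protocol?** In protocol Section 8, "At Weeks 16 and 32, the visit window can be extended by 7 additional days" for CFR. The Week 16 CFR window is 113 - 7 = Day 106 to 113 + 14 = Day 127, and the Week 32 window is Day 218 to Day 239. Both lie inside Table 2's CFR rows. Apart from final visits, the Week 20 label reaches only readings from Day 130 on, at least three days past the protocol limit.

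**4. Final visits after termination.** Final visit = last dose day + 28 to + 56, taking doses on their target days.

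| Last dose | Final visit by footnote c | CFR label by study day in Table 2 |
|---|---|---|
| Week 12 (Day 85) | Days 113 to 141 | Week 16 on Days 113 to 129 (17 days); Week 20 on Days 130 to 141 (12 days) |
| Week 20 (Day 141) | Days 169 to 197 | Week 20 on Day 169; Week 28 on Days 170 to 197 |
| Week 28 (Day 197) | Days 225 to 253 | Week 32 throughout |

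The two definitions agree after a Week 28 last dose. They disagree on every day of the Week 12 and Week 20 ranges.

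**5. S2.** Before dosing, study day is the date minus the first-dose date. The protocol allows S2 up to 4 weeks before Week 0, which is Day -28. Table 2 opens the row at Day -27. That row is shared with the pregnancy test, whose S1 window ends at Day -28, which may explain the start. Cardiology is not measured at S1, so nothing needs to be set aside for it.

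**The case against.** The strongest reply is that the SAP already handles early final visits. Footnote c and Appendix 2 show that the sponsor means to analyse them as Week 32, and if footnote c is programmed as overriding, none of them is lost. That stands. A reader might infer that CFR readings after a Week 12 or Week 20 last dose will drop out of the primary analysis; the documents do not support this. What they lack is a sentence saying which part of Table 2 wins.

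A second reply is that the general Week 20 and Week 28 rows do not really claim GLS and cfPWV, because the combining sentence exists to modify general rows. That is a fair reading and it also stands. It does not rescue the CFR rows, which are specific to that measure.

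A reader might also infer that GLS and cfPWV on Days 126 to 127 are permitted Week 16 readings sent to Week 20. Only the Schedule of Activities header supports +14 days for the whole visit. Protocol footnote g and SAP footnote b tie the extra 7 days to CFR. Without them the window ends at 113 + 7 = Day 120, inside the general row.

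Finally, one could argue for letting study day override footnote c. That would reverse Appendix 2 and could discard data. With a Week 16 CFR on Day 113 and a final visit on Day 141, both fall in Days 58 to 169 and the closest-to-target rule drops the final visit. Days 2 to 57 would also have no post-baseline window, although a final visit after a Week 0 last dose falls on Days 29 to 57.

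**Conclusion.** Wrong as written, in three limited respects.

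- Table 2's CFR Week 20 row contradicts Section 5.1.1. It affects CFR readings on Days 130 to 169 that are not final visits, all of them later than the protocol allows.
- For final visits after termination the SAP gives two answers without ranking them: Days 113 to 141 after a Week 12 last dose and Days 169 to 197 after a Week 20 last dose. This is conflicting assignment, with Week 32 the evident intent.
- The S2 cardiology window is one day too short. This bears only on the S2-versus-Week 0 comparison, since the cardiology baseline comes from Days -13 to 1.

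The ranges assume doses on their target days. The counts are calendar days, not readings: the documents give no actual visit dates, so neither the number of readings affected nor the effect on the estimate can be computed. Whether an early final visit ought to represent Week 32 at all is a separate question.

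**What to change.** In SAP Section 5.1.1 and Table 2:

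1. Delete the CFR Week 20 row.
2. Give CFR, GLS and cfPWV their own combined windows for readings that are not Final Efficacy Visits, with the cut between Week 16 and Week 32 at Day 169. The CFR rows at Weeks 16 and 32 must change with it; otherwise Days 130 to 210 are left without a CFR-specific row. Write out the lower end of Week 16 (Day 58 under the midpoint rule) and keep an upper end for Week 32.
3. State that footnote c takes precedence, so a reading from a Final Efficacy Visit is analysed as Week 32, as Appendix 2 says. Tie this to visits carried out as Final Efficacy Visits, because an ordinary Week 16 visit on Day 113 is also 28 days after a Week 12 dose on Day 85.
4. Set the S2 cardiology window to Day -28 to -14.

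The cost is a table edit and reprogramming of the analysis visits. Some Week 16 values will lie further from Day 113, so actual study days should be listed beside them.
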